## Statistical Analysis

In a study that was conducted by Seet et al., power was calculated as 90% as a result of the power analysis that was made for laryngeal mask airway  $OLP = >21 +/- 5 \text{ cmH}_2\text{O}$  average values; and the number of the case was determined to be 40 for each group (30).

The data have been evaluated with the SPSS (Statistical Package for Social Sciences) 15.0 package program. The fitness of the variables to normal distribution was tested with the Kolmogorov Smirnov Test. The t-test was used to compare the two groups that fit normal distribution; and the Mann Whitney U-Test was used for those that did not fit normal distribution. The variables that were defined with numbers were evaluated with the Chi-Square Test and with the Fisher's Exact Test when needed; and the significance level was taken as  $p < 0.05$ . The mean, standard deviation, median, min. and max. values of the continuous variables and their sub-groups were presented; and the frequency numbers and percentages of the class variables were presented.

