## **MATERIAL AND METHOD**

This study will be completed after receiving permission from "Dokuz Eylül University Faculty of Medicine Clinical Research Ethics Committee" and "Medical Device Study and Authorization Coordination Department", (Protocol No: 266-SBKAEK) with informed patient consent, as a prospective, randomized and double-blind study of 102 patients in ASA classification group I-II, aged from 18 to 65 years undergoing elective laparoscopic gynecological surgery.

Patients will be divided as

Group 1 => i-gel (51 patients) (control group)

Group 2 => LMA-Supreme (51 patients) (experiment group).

Patients and surgeons performing the operations will not be aware of the airway device used. Patients in the groups will be determined with the block randomization method. By looking at a simple random number table, 102 individuals will be divided into 2 groups of 51 by using 6 blocks of groups containing.

Before anesthesia induction patients taken to the operating room will have standard monitoring applied (non-invasive blood pressure measurements, electrocardiogram, peripheral oxygen saturation measurements). For preoperative sedation 0.02 mg/kg midazolam IV will be administered. Patients will be preoxygenized for 3 minutes with 6 L/min oxygen through a face mask. For anesthesia induction after 2 minutes of 0.2  $\mu$ kg/min remifentanil and 6 mg kg propofol infusion, IV 1-2 mg kg propofol will be administered. After induction patients will be ventilated with a face mask with 6 L/min 100% oxygen.

All patients will have bispectral index monitoring (BIS, ASPECT A-2000 BIS XP monitor) to standardize anesthesia depth. BIS values will be held between 40-60. BIS values will be kept within this interval by increasing or decreasing propofol infusion by 1 mg/kg after additional bolus dose of propofol (1 mg/kg).

Airway device insertion will be performed by two researchers with more than 5 years experience.

During airway device insertion, if necessary depending on patient reaction additional doses of 0.5 mg/kg propofol will be administered.

Anesthesia maintenance will be ensured by 50% O2/air with 0.1-0.4  $\mu$  kg/min remifentanil and 50-150  $\mu$  kg/ min (4-10 mg/kg/hr) propofol IV infusion (29).

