Before inserting the LMA-Supreme and i-gel, water-based K-YTM (*Johnson & Johnson Ltd. Maidenhead, UK*) gel, not containing local anesthetic material, will be spread on surfaces that will come in contact with the palate. Depending on body weight of patients LMA-Supreme numbered as follows will be inserted:

for < 50 kg: 3

50-70 kg: 4 6

70-100 kg: 5

Again depending on body weight of patients, i-gel numbered as follows will be inserted:

30-60 kg: 3

50-90 kg: 4

>90 kg: 5.

Successful insertion of LMA-Supreme or i-gel will be confirmed by square-shaped waves on capnogram, easy ventilation with respiration balloon and observation of chest movements. After confirming successful emplacement of airway device with fiberoptics, later to prevent observation of the device it will be covered. Laryngeal view will be assessed with points from 1 to 3 by the anesthesiologist (complete vocal cords view, non-obstructing epiglottis view and obstructed view).

**For successful insertion** duration (time from mouth-opening to first successful ventilation), number of attempts and ease of insertion will be recorded. Ease of insertion will be assessed as easy, difficult or unsuccessful (alternative airway management) by the anesthetist securing the airway (6,30).

In situations with 3 unsuccessful attempts at securing the airway, patients without LMA-Supreme or i-gel insertion will have airway management ensured with endotracheal intubation. **For oropharyngeal leak test** after shutting the expirium valve, air will be closed and O2 flow reduced to 3 L/min and the first pressure value when a leak sound is heard from the mouth will be recorded as oropharyngeal leak pressure. To prevent exposure of lungs to barotrauma, when peak inspiratory pressure (*peak*) of 40 cmH2O is reached the expiratory valve will be opened and the test ended (30). This test will be performed before peritoneal insufflation, 10 minutes later and immediately before desufflation and will be completed by a researcher blind to the type of airway device.

We considered the concept “margin on oropharyngeal leak pressure (OLP)” (MOLP), defined as the value for the margin of pressure between the highest PAW-pk during pneumoperitoneum and the maximum safety’s seal pressure value (SP). Our purpose is try to assess the “safety gap” on our patient’s airway (in terms of pressure) until it reaches the maximum PAW-pk permitted value under safety conditions (SP) (37).

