**Exclusion Criteria:**

- 1. Those with any neck or upper respiratory tract pathology
- 2. Those at risk of gastric content regurgitation/aspiration (previous upper Gastrointestinal system surgery, known hiatus hernia, gastroesophageal reflux, history of peptic ulcers, full stomach, pregnancy)
- 3. Those with low pulmonary compliance or high airway resistance (chronic pulmonary diseases)
- 4. Obese patients (BMI >35)
- 5. Those with throat pain, dysphagia and dysphonia
- 6. Those with possible or previous difficult airway
- 7. Those with operations planned for longer than 4 hours

8. Conversion to laparotomy

9. Neuromuscular blocking agent used

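### The continuous outcomes are compared without adjustment although BMI must be obtained for every patient; the tests are valid, but the device estimates may be less precise than the data allow.

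*Combined protocol and SAP*

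**What the plan says.** The Statistical Analysis section names two tests for continuous outcomes. The first depends on a normality check: "The t-test was used to compare the two groups that fit normal distribution". Outcomes that fail the check go to a Mann-Whitney test, which takes no covariates. Categorical outcomes go to chi-square or Fisher tests. No covariate, regression or analysis of covariance is mentioned. Material and Method describes block randomisation into two groups of 51 and names no stratification factor.

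Body size enters the plan elsewhere. Exclusion criterion 4 reads "Obese patients (BMI >35", so BMI has to be worked out for every candidate. Body weight also decides the device size: "Depending on body weight of patients LMA-Supreme numbered as follows will be inserted", with a separate weight table for the i-gel.

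On who places the device, Material and Method says: "Airway device insertion will be performed by two researchers with more than 5 years experience". It does not say that the inserter is recorded for each patient, or how that person is chosen.

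**The concern.** The outcomes at issue are OLP, the margin between the seal pressure and the highest peak airway pressure (MOLP), Ppeak and Pmean. Most are measured under pneumoperitoneum at 15 mmHg with Trendelenburg positioning, where a link with body habitus is plausible. The protocol itself treats habitus as relevant by excluding high BMI and sizing devices by weight.

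A pre-device value of the outcome would normally be the best covariate, but none can exist here because the first leak test follows insertion. A patient characteristic such as BMI is the natural substitute.

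If BMI explains part of the outcome variance, an unadjusted test leaves that part in the error term and the interval for the device difference is wider than it need be. Any chance difference in BMI between the arms also stays in the point estimate of this particular trial. If adjustment is considered only after such an imbalance is seen, the choice is data-driven. That is the reason to settle it in advance.

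**Working it through.** **Inputs from the documents**
- 51 patients per arm, 102 in total (Material and Method).
- For OLP, a mean above 21 with ±5 cmH2O (Statistical Analysis). The 5 is not labelled; it is read here as the SD.
- Significance level 0.05, sidedness not stated; two-sided is assumed.
- Sample size statement: "power was calculated as 90" per cent, and "the number of the case was determined to be 40 for each group".

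**Assumed input**
- r, the within-arm correlation between BMI and the outcome. The documents give none, so it is varied from 0 to 0.5.

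**Step 1: the plan's own figure.** The 40 per group cannot be reproduced, because no target difference is stated. Solving backwards with the normal approximation:

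difference = SD × (1.960 + 1.282) × √(2/n) = 5 × 3.242 × √(2/40) = 3.62 cmH2O.

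At that implied difference, 51 per arm gives about 95% power with the unadjusted t-test (95.2% by the noncentral t, 95.5% by the normal approximation).

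**Step 2: unadjusted precision with 51 per arm.**

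SE = 5 × √(2/51) = 0.990. Half-width = t(0.975; 100 df) × SE = 1.984 × 0.990 = 1.964 cmH2O.

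**Step 3: precision with BMI in a linear model.** The residual SD is 5 × √(1 − r²). Estimating one covariate inflates the variance by about 1 + 1/(102 − 1 − 3) = 1 + 1/98, and the residual df fall to 99:

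half-width = 1.984 × 0.990 × √(1 − r²) × √(1 + 1/98) = 1.975 × √(1 − r²).

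| r | √(1 − r²) | Half-width (cmH2O) | Change from 1.964 |
|---|---|---|---|
| 0 | 1.000 | 1.975 | 0.5% wider |
| 0.1 | 0.995 | 1.965 | none |
| 0.2 | 0.980 | 1.935 | 1.5% narrower |
| 0.3 | 0.954 | 1.884 | 4.1% narrower |
| 0.4 | 0.917 | 1.810 | 7.9% narrower |
| 0.5 | 0.866 | 1.710 | 12.9% narrower |

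**Step 4: break-even.** The two half-widths are equal when 1 − r² = (t(100 df)/t(99 df))² / (1 + 1/98), which gives r² = 0.0103, or r of about 0.10.

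**Step 5: power at the implied difference of 3.62 cmH2O** (noncentral t, with the covariate penalty): 95.2% unadjusted; with BMI 95.0% at r = 0, 95.7% at r = 0.2, 96.6% at r = 0.3 and 98.6% at r = 0.5.

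**Step 6: chance imbalance.** The standardised BMI difference between arms has standard error √(2/51) = 0.198. A difference of 0.3 SD or more in either direction (0.3/0.198 = 1.515) has probability about 13%. It would move the OLP difference by 0.3 × r × 5, that is 0.45 cmH2O at r = 0.3 and 0.75 cmH2O at r = 0.5.

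All of this is for OLP. The documents give no SD for MOLP, Ppeak or Pmean, but the percentage changes in Step 3 depend only on r and apply to them equally.

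**The case against.** The strongest reply is that nothing is wrong with the plan. Under randomisation the t-test is valid, and its standard error already allows for chance imbalance in BMI. That stands: a reader might infer from Step 6 that the planned estimate is biased, and it is not.

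A reader might also infer that precision is certainly being lost. The documents do not support that, because they give no correlation. Design features may keep it low: very obese patients and those with low compliance or high resistance are excluded, device size follows weight, and tidal volume is set per kilogram. At r = 0.2 the gain is only about 1.5%, and below about 0.10 there is none.

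Nor do the plan's figures show a power shortfall for OLP. At the difference they imply, 51 per arm already gives about 95%. Lower power at some smaller difference would rest on a target that the documents do not state.

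It is also tempting to say that the inserter is known for every case and should go into the model. The text establishes only that two researchers place the devices. It does not say that the identity is recorded, or fixed before allocation is known. An inserter chosen after allocation would not be a baseline covariate.

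What survives is narrower. BMI has to be obtained for every patient, the planned analysis does not use it, and the trade is lopsided: about 0.5% wider at worst, against about 4% to 13% narrower if r is 0.3 to 0.5.

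**Conclusion.** The point holds as an efficiency recommendation, not as an error or a bias. The planned comparisons are unadjusted, BMI is needed for eligibility, and the device estimates may therefore be less precise than the data allow. For OLP the effect on the 95% interval half-width runs from 1.964 to 1.975 cmH2O if BMI is irrelevant, and down to 1.710 if r is 0.5.

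This rests on reading 5 cmH2O as the SD, a two-sided 0.05 level, all 51 per arm being analysed, a roughly linear BMI effect, and values of r that are assumed. The case for BMI does not depend on the inserter, for whom the documents do not establish usable baseline information.

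**What to change.** In the Statistical Analysis section, prespecify for OLP, MOLP, Ppeak and Pmean a linear model with arm and continuous BMI, at each planned time point (for MOLP, over the period that defines it). Report the adjusted device difference with its 95% confidence interval. Keep the t-test or Mann-Whitney test as a sensitivity analysis, and say that the linear model is the main analysis for these four outcomes, so that the normality test does not decide which result leads.

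Do not adjust for device size: the weight bands differ between the devices, so size follows from the allocated device. Add the inserter only if that person is recorded for each case and named before the allocation is opened; this would need a form field and a procedural step that the protocol does not now describe.

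The section is written in the past tense. If outcome data by arm have already been examined, the adjusted analysis should be labelled post hoc.

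The cost for BMI is SAP wording and one degree of freedom, with no additional patients, measurements or procedures.

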## **AIM**

To compare the effects of i-gel and LMA-Supreme on ventilation parameters and surgical view during laparoscopic gynecological surgery in cases administered positive pressure ventilation without the use of neuromuscular agents.

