Positive pressure respiration using a ring system will begin with 2-4 L/min fresh gas flow and FiO2 0.5 volume control with 6-8 ml/kg tidal volume and 10 respirations/min frequency.

PEEP will not be applied and I:E ratio will be 1:1,5. ETCO2 will be held from 35-45 mmHg, if necessary first respiration frequency will be increased, later tidal volume will be increased. For laparoscopic intervention, permission will be given for CO2 insufflation for peritoneal interior pressure of 15 mmHg.

Two minutes after insertion of LMA-Supreme or i-gel, before insufflation, 10 minutes after insufflation and trendelenburg position, immediately before peritoneal desufflation and before removing the airway device, ventilation parameters will be assessed.

**Respiratory Measurements recorded:** Tidal volume (TV), respiration rate (RR), peripheral oxygen saturation (SPO2), end-tidal carbon dioxide pressure (PETCO2), peak airway pressure (Ppeak), mean airway pressure (Pmean) and expiratory volume per minute (VE).

**Hemodynamic Measurements recorded:** (Simultaneous to the above measurements and additionally before induction) systolic arterial pressure (SAP), diastolic arterial pressure (DAP), mean arterial pressure (MAP), and heart rate (HR).

**Evaluation related to stomach probe:** Immediately after the airway device is inserted, through the LMA-Supreme (14F for size 3 and 16F for sizes 4 and 5) and i-gel drainage tube a 12F orogastric tube will be advanced to the stomach and stomach contents aspirated. The ease of insertion of stomach probe and amount of aspirated fluid will be recorded. Ease of insertion of orogastric tube will be classified as very easy, easy, difficult or very difficult by the administrator (9). Gastric aspiration will be 200 cmH2O during 10 seconds by a suction; (connecting it later to a collection bag).

The number of interventions of verres needle, initial intra-abdominal pressure, time for intra-abdominal pressure to reach 15 mmHg, and volume of insufflated CO2 will be recorded. Sufficiency of pneumoperitoneum during operation (sufficient/insufficient), and quality of surgical view will be assessed with points from 1 to 4 by the surgeon blind to the airway device (24).

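### The plan names no test for its ordered grades, including surgical view, which is in the aim; name Mann-Whitney for them in advance

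*Combined protocol and SAP*

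**What the plan says.** The Statistical Analysis section assigns no named outcome to a test. It has three routes:

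- a t-test for variables that fit a normal distribution;
- for the rest, "the Mann Whitney U-Test was used for those that did not fit normal distribution";
- a third route: "The variables that were defined with numbers were evaluated with the Chi-Square Test", with "Fisher's Exact Test when needed".

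For reporting it recognises two kinds of variable. Continuous variables get means, standard deviations, medians and ranges. For the other kind, "the frequency numbers and percentages of the class variables were presented". Ordered grades are not mentioned.

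The Aim reads: "To compare the effects of i-gel and LMA-Supreme on ventilation parameters and surgical view during laparoscopic gynecological surgery". Material and Method then defines four outcomes on ordered scales:

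- Surgical view: "quality of surgical view will be assessed with points from 1 to 4 by the surgeon blind to the airway device".
- Laryngeal view: "Laryngeal view will be assessed with points from 1 to 3 by the anesthesiologist", with the same three grades also described in words.
- Orogastric tube: "Ease of insertion of orogastric tube will be classified as very easy, easy, difficult or very difficult by the administrator".
- Blood on the device after removal: three numbered levels, from none to clear amounts.

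Ease of device insertion is also graded, but its third level is failure with a change to another airway, so it is not simply an ordered grade.

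Arterial pressures and heart rate are recorded before induction as well as at the later time points. The section specifies no use for the pre-induction values.

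**The concern.** Surgical view is one of the two things the aim sets out to compare, and the plan leaves two candidate tests for it. They can give different p-values on the same table, and nothing in the plan prevents the choice from being made after the data are seen.

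The candidates also ask different questions. Chi-square and its exact counterpart ask whether the grade shares differ in any way. Mann-Whitney asks whether one device tends to give better grades. If one device moves patients along the whole scale, the order-blind test spreads the signal over several degrees of freedom and loses power.

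The scoring format does not settle which route applies. Laryngeal view is given both as points and as worded categories, and tube insertion only in words.

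**Working it through.** **Plan's own figure.** There is none to reproduce here. The only sample-size statement concerns oropharyngeal leak pressure. No power, grade distribution or effect is given for any graded outcome.

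**Inputs from the documents.** 51 per arm (Material and Method), significance level 0.05 (Statistical Analysis), four-point and three-point scales.

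**Assumptions.** Two-sided testing. Control shares of 50/30/15/5% or 80/15/4/1% over four grades. A common odds ratio (OR) of 1.5 to 4, in either direction. Fisher's exact test is taken to be needed when any expected count is below 5.

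**Example by formula: 50/30/15/5%, OR 2.5 towards worse.**

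1. Cumulative odds of 1, 4 and 19, divided by 2.5, give 0.4, 1.6 and 7.6. The shifted shares are 28.6/33.0/26.8/11.6%.
2. Chi-square noncentrality is n·Σ(p−q)²/(p+q) = 51 × (0.0585 + 0.0014 + 0.0334 + 0.0264) = 6.1. On 3 degrees of freedom (critical value 7.815), power is about 53%.
3. Mann-Whitney: θ = P(higher grade) + ½P(tie) = 0.634. With p̄ the average shares, the null standard error is √[(1 − Σp̄³)/(6n)] = √[(1 − 0.1016)/306] = 0.0542. So z = 0.134/0.0542 = 2.47, and power is Φ(2.47 − 1.96), about 70%.

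The squared z is also 6.1. Mann-Whitney places essentially all the signal on one degree of freedom, and chi-square spreads it over three.

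**Simulation** (8,000 trials per scenario, Monte Carlo error at most 0.6 points), power in %:

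| Control shares, direction | OR | Pearson | Chi-square/Fisher | Mann-Whitney | Loss, Pearson | Loss, chi-square/Fisher |
|---|---|---|---|---|---|---|
| 50/30/15/5, worse | 1.5 | 12.4 | 13.0 | 19.2 | 6.8 | 6.2 |
| 50/30/15/5, worse | 2.5 | 53.8 | 54.0 | 71.3 | 17.5 | 17.3 |
| 50/30/15/5, worse | 4 | 89.9 | 89.9 | 96.6 | 6.7 | 6.7 |
| 80/15/4/1, worse | 2.5 | 37.6 | 42.3 | 55.6 | 18.0 | 13.3 |
| 80/15/4/1, better | 1.5 | 6.7 | 9.2 | 11.6 | 4.9 | 2.4 |
| 80/15/4/1, better | 4 | 39.5 | 46.3 | 58.4 | 18.9 | 12.1 |

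The largest and smallest chi-square/Fisher losses and the largest Pearson loss over all scenarios are in this table. With three grades (60/30/10% or 85/12/3%) the loss is about 3 to 12 points. With only two grades in use, Pearson and Mann-Whitney agree.

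**Where the order reverses.** Keep 50/30/15/5% and move patients only from grade 2 to grade 3: 50/10/35/5%.

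- Chi-square noncentrality is 51 × (0.04/0.4 + 0.04/0.5) = 9.18.
- For Mann-Whitney, θ = 0.545 and z = 0.045/0.0527 = 0.85, so z² is only about 0.7.
- Simulated power is 74% for chi-square and 14% for Mann-Whitney.

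A shift only from grade 1 to grade 2 (30/50/15/5%) gives 46% and 33%. A non-monotone difference (65/10/10/15%) gives 74% and 12%.

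**Secondary point, haemodynamics.** Adjusting for a baseline with correlation r multiplies the residual variance by 1 − r². Unadjusted power of 80% (assumed) corresponds to 1.960 + 0.842 = 2.802.

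- r = 0.3: 2.802/√0.91 = 2.937, power Φ(0.977) = 84%.
- r = 0.5: 2.802/√0.75 = 3.235, power Φ(1.275) = 90%.
- r = 0: no gain.

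The documents do not give r.

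**The case against.** The strongest objection is that the gap may not exist for the outcome that matters most. Surgical view is a point score. A four-point score will hardly pass a normality test, and the plan sends variables that fail it to Mann-Whitney, which is the test recommended here. This stands as a possible reading, and under it no power is lost. It does not close the gap: the chi-square sentence fits the same score equally well, and the plan does not choose.

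A second objection is that the power advantage is not general. This also stands. A reader might infer that Mann-Whitney wins whenever one device is consistently worse. The grade 2 to grade 3 example is a pure worsening, and there chi-square is far stronger. The advantage is shown for a shift with a common odds ratio across the scale.

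Third, the largest Pearson loss comes from a sparse distribution in which Pearson's null rejection rate is only 2.8%, against 4.7% for Mann-Whitney. Part of that gap is therefore conservatism and not ignored order. Fisher would be triggered in 52 to 99% of four-grade trials at OR 1 to 3, so the chi-square/Fisher figures are the more relevant ones.

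Finally, chi-square/Fisher brings no bias and no inflated error rate, and the sample size was not set on a graded outcome. Both points are right, and they limit the matter to clarity and power. The haemodynamic adjustment likewise concerns precision only, on outcomes outside the aim; the unadjusted comparison is valid.

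**Conclusion.** The concern holds in a limited form. The plan does not say how ordered grades will be tested, although one of them is named in the aim. Chi-square/Fisher is a plausible reading and Mann-Whitney a possible one. If chi-square/Fisher is used and the devices differ by a common-odds-ratio shift, the cost at 51 per arm is about 2 to 17 power points for four grades under the assumed Fisher rule, and up to about 19 for Pearson chi-square alone. These sizes rest on assumed grade shares and odds ratios of 1.5 to 4.

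A stronger conclusion is tempting: that the plan commits to an order-blind test and will lose power against any one-directional difference. The documents do not support it. The text leaves the test open, and without grade shares or an expected effect even the sign of the power difference is unknown. The firmer reason to act is that a test named in advance removes a choice on an aim-level outcome, and that Mann-Whitney matches the question of whether one device gives generally better grades.

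**What to change.** In Statistical Analysis:

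- State that surgical view, laryngeal view, ease of orogastric tube insertion and blood grade will be compared between groups by the Mann-Whitney test, with counts and percentages reported for every grade.
- Keep chi-square/Fisher for binary and unordered variables.
- Report insertion failure as its own binary outcome.
- Secondary: analyse later arterial pressures and heart rate by ANCOVA with the pre-induction value as covariate.

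The cost is two or three sentences and no new data. The drawback is lower power for differences that are non-monotone or confined to two grades. The per-grade counts would still show such a pattern, though the test might not detect it.
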